5.1 Assignment of analysis sets

Full analysis set (FAS)

All patients who were randomized to treatment arms at the start of the study will be included in the FAS. Protocol deviation, demographics, baseline characteristics, medical history, prior and concomitant medication, prior and concomitant anti-cancer therapy will be summarized in the FAS.

Safety analysis set (SAF)

All patients with at least one administration of study drug will be included in the SAF. The SAF will be used for the analyses of study drug exposure, safety and efficacy variables.

All patients with valid pharmacokinetic (PK) data may be analyzed in the evaluation of PK concentrations and parameters.

Patients who signed the informed consent but were not assigned to treatment will be considered screening failures. They will be listed separately.

6. Statistical Methodology

Disposition, protocol deviations, demographics, baseline cancer characteristics, medical history, prior and concomitant medication, prior and concomitant anti-cancer therapy, drug exposure, efficacy and safety variables will be summarized separately for 2 groups including patients

- who were randomized to copanlisib until the end of study (copanlisib group)
- who were randomized to placebo until switching from placebo to copanlisib after PD or after unblinding (placebo group)

Disposition, protocol deviations, concomitant medication, concomitant anti-cancer therapy, drug exposure, efficacy and safety variables will also be summarized separately for patients who switched from placebo to copanlisib.

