The start of the treatment period is defined by first administration of study drug (Copanlisib or placebo). Copanlisib will be administered IV over approximately 1h at starting dose of 60 mg on Days 1, 8 and 15 of each 28-day treatment cycle. Treatment will be continued until progressive disease (PD) by radiological assessments or clinical progression (tumor evaluations will be made at intervals that comply with the institution's standard of care [per investigator's assessment]), unacceptable toxicity, or until another criterion is met for withdrawal from the study treatment. Before unblinding, patients in the placebo arm will receive a placebo IV infusion at the same schedule as that of Copanlisib arm. However, when placebo patients had PD before unblinding cut-off, they can choose to switch to Copanlisib and continue to stay in the study.

Disease progression (PD) defined in the Lugano Classification (3) and the Owen criteria (4) for patients with WM will be assessed.

Statistical Analysis Plan

BAY 80-6946 / 17322

Page: 8 of 20:

All patients, after unblinding procedures are completed, will be offered an opportunity to continue this clinical study and receive active treatment with Copanlisib. Patients who are on Copanlisib treatment at the time of unblinding will continue Copanlisib treatment. Patients who are on placebo at the time of unblinding will switch to Copanlisib treatment after unblinding procedures are completed. After individual patient unblinding, patients receiving placebo, who switch to Copanlisib will have all study assessments reset to the initial schedule of study evaluations (i.e. as if the patient was restarted the study at Cycle 1 Day 1).

An End-of-treatment (EOT) visit will be performed within 7 days after the decision is made to discontinue study treatment.

Safety Follow-up Period

Following completion of the EOT visit, patients will enter the Safety follow-up. The Safety follow-up (SFU) visit will take place 30 days (window of +5 days allowed) after the last administration of study drug.

All patients who have already completed the safety follow-up visit at the time the amendment 6 becomes effective will discontinue the study.

4. General Statistical Considerations

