4.1 General Principles

Statistical analyses will be conducted by or under the supervision of the sponsor's Study Statistician, except for the analysis of biomarker data, which, if considered to be performed, will be performed by or under the direction of the sponsor's Genomics and Biomarker Statistical Expert. Statistical analyses will be performed by using the software package Statistical Analysis System (SAS) release 9.2 or higher (SAS Institute Inc., Cary, NC, USA).

Due to the decision of stopping enrollment, limited number of patients will be included in the analyses. Therefore, the statistical analyses included in this study will be focused on descriptive statistics on safety variables only. The number of data available and missing data, mean, standard deviation, minimum, quartiles, median, and maximum will be calculated for metric data. Frequency tables will be generated for categorical data.

Definition of safety endpoints, analyses strategies, structure of analyses datasets and layout of analyses data displays are following Bayer standards as documented in the Bayer standard system: Clinical Copanlisib Project Standards, Oncology Therapeutic Area Standards, and Global Medical Standards, respectively. Where the given ordering reflects the priority of the different standards that is specifications of the latter ones have to be followed only if not specified in standards mentioned before. Study-specific specifications may be included in addition to the project standards, if needed.

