6.1.8 Study Drug Administration

Descriptive statistical summaries of study drug exposure will be provided for the following variables:

- Overall extent of exposure (OEE) in days:

Defined as the time from the first administration of the first study treatment (day_{first}) until the last administration of the last study treatment (day_{last}), including 7 additional days in order to consider the weekly dosing regimen, is calculated as:

$$\text{OEE (days)} = \text{day}_{\text{last}} - \text{day}_{\text{first}} + 7.$$

- Number of cycles
- Number of infusions during treatment phase and categorized by 1-6, 7-12, 13-18 and etc.
- Total dose actually administered (mg)

OEE will include interruptions/delays during treatment. As a general rule, and in accordance with the Therapeutic Area Standard oncology team and the timing concept, trailing “0 mg” records (not followed by any positive amount of drug), will not be included in the calculation of any drug duration or amount. Similarly, the according trailing “drug interruptions” will not be used in statistical tables. A footnote will be included, stating that “Interruption becoming permanent study treatment discontinuation before resumption of study treatment is not accounted as an interruption”.

For patients with dose modification, the total number (%) of subjects with dose reductions, interruptions/delays, re-escalations and the total number (%) of dose reductions, interruptions/delays, re-escalations and the reasons will be summarized. Number of reduction, interruption/delay and re-escalation per subject will also be summarized.

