6.3.1 Adverse Events

Adverse Events (AEs) will be coded using *Medical Dictionary for Regulatory Activities* (MedDRA) dictionary Version 22.1. Severity of AEs will be graded using the NCI-CTCAE v4.03. AEs will be classified by the investigator as related or not related to study drug.

Treatment emergent adverse events (TEAEs)

TEAEs are defined as any event arising or worsening after start of study drug administration until 30 days (window of +5 days allowed) after the last study drug administration (end of Safety follow-up). More specifically, for the patients who received Copanlisib until the end of study and the patients who received placebo until switching to Copanlisib after PD or after

Statistical Analysis Plan

BAY 80-6946 / 17322

Page: 15 of 20:

unblinding, the start of study drug administration is referring to the start of Copanlisib or placebo after randomization. For the patients switching from placebo to Copanlisib, the start of study drug administration is referring to the start of Copanlisib drug administration after switching. See Section 4.3 for handling of partial dates for AEs. In the case where it is not possible to define an AE as treatment-emergent or not, the AE will be classified by the worst case; i.e. treatment-emergent.

An overall summary of the following TEAEs by MedDRA (SOC) and (PT) will be provided for safety analysis set:

- Any TEAEs
- Any treatment emergent serious adverse events (TESAEs)
- Any TEAEs leading to discontinuation
- Any TEAEs leading to dose modification
- Any TEAEs related to protocol procedure
- Any study drug related TEAEs
- Any study drug related treatment TESAEs
- Any study drug related TEAEs leading to discontinuation
- Any study drug related TEAEs leading to dose modification

The following will be summarized by MedDRA system organ class (SOC) and preferred term (PT), and by worst grade based on Common Terminology Criteria Adverse Event (CTCAE) v. 4.03.

- TEAEs
- TEAEs with incidence $\geq 10\%$
- Grade 3-5 TEAEs
- Treatment related TEAEs
- Treatment related TEAEs incidence $\geq 5\%$
- Grade 3-5 treatment related TEAEs
- TESAEs
- Grade 3-5 TESAEs
- Treatment related TESAEs
- Any TEAEs leading to discontinuation
- Any TEAEs leading to dose interruption
- Any TEAEs leading to dose reduction
- Any drug related TEAEs leading to discontinuation
- Any drug related TEAEs leading to dose interruption
- Any drug related TEAEs leading to dose reduction

Statistical Analysis Plan

BAY 80-6946 / 17322

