Page: 16 of 20:

The maximum severity of the TEAEs will be summarized according to the NCI-CTCAE toxicity criteria. For each patient, multiple occurrences of the same event will be counted once at their maximum severity within a SOC and PT.

Adverse Events of Special Interest

Non-infectious Pneumonitis is defined as AE of special safety interest. The Standardized MedDRA Query (SMQ) 'Interstitial lung disease' with narrow search (i.e. category 2A) will be used to select these AEs of special interest. The only relevant NCI CTCAE code is AETOXCOD=RTPNM (pneumonitis).

Summary of patients with Non- infectious pneumonitis/Interstitial lung disease requiring corticosteroids, antibiotics, or both will be displayed descriptively. All patients with TEAEs of special interest by worst CTCAE grade, study drug relatedness and seriousness will be listed.

COVID-19 relevant adverse events

The COVID-19 relevant adverse events will be identified using a high-level term (HLT) of coronavirus infection via latest MedDRA version. A subject listing of these AEs will be provided. The serious AEs will be flagged in the listing.

AE listings

Subject listings will be provided for serious TEAEs, TEAEs leading to discontinuation, TEAEs leading to interruptions and reductions and TEAEs of special interests including the worst CTCAE grade, study drug relatedness, and seriousness.

Death

Summary table and listings will be provided for

- Subjects who died during treatment or up to 30 days (window of +5 days allowed) after last dose of study medication
- Subjects who died later than 30 days (window of +5 days allowed) after last dose of study medication

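### Cumulative safety tables run copanlisib to end of study but placebo only to the switch, and the SAP plans no summary limited to the period before unblinding

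*SAP*

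**What the plan says.** SAP Section 6 defines two groups for the safety summaries: patients "who were randomized to copanlisib until the end of study (copanlisib group") and patients "who were randomized to placebo until switching from placebo to copanlisib after PD or after unblinding (placebo group"). A further summary covers placebo patients after they move to copanlisib.

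The treatment period text in Section 3 explains what happens at unblinding. For the active arm, "Patients who are on Copanlisib treatment at the time of unblinding will continue Copanlisib treatment". For the placebo arm, "After individual patient unblinding, patients receiving placebo, who switch to Copanlisib will have all study assessments reset to the initial schedule".

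The counting rules are cumulative:
- Section 6.3.1: "TEAEs are defined as any event arising or worsening after start of study drug administration until 30 days" after the last dose. For severity, "For each patient, multiple occurrences of the same event will be counted once at their maximum severity within a SOC and PT".
- Section 6.3.3 tabulates the worst post-baseline laboratory grade.
- Section 6.3.4 tabulates hyperglycemia TEAEs by treatment group and worst grade.

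Section 7 records that the protocol's unblinding analysis (cut-off 1) and final analysis (cut-off 2) were merged into this single set after discussion with Regulatory. The content of cut-off 1 is not shown. Section 4.1 limits the scope: "the statistical analyses included in this study will be focused on descriptive statistics on safety variables only". Section 6.1.8 adds: "Descriptive statistical summaries of study drug exposure will be provided for the following variables", and Section 6 applies these summaries to the same groups.

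**The concern.** A proportion of patients with at least one event, or a worst grade per patient, can only rise as observation lengthens. The copanlisib column keeps accumulating after unblinding for every randomized copanlisib patient still on drug. The placebo column closes at the switch. The copanlisib column also mixes events reported under blinding with events reported when investigator and patient knew the treatment.

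Safety is the study's only stated objective, and no model or test stands between the raw percentages and the reader. Anyone who sets the two columns side by side will take part of the difference for a drug effect when it comes from window length or open-label reporting. The SAP text offers no like-for-like blinded comparison of these cumulative results.

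**Working it through.** **Which tables are affected.** TEAE incidence and maximum severity (6.3.1), worst post-baseline laboratory grade (6.3.3) and hyperglycemia TEAEs by worst grade (6.3.4) accumulate over the whole window. Laboratory values and vital signs by visit, and glucose grades by visit, are aligned in time and are not affected.

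**What the planned output can already separate.** The exposure table shows that the windows differ, but not which events fell in the added time. Section 6.3.1 plans listings of deaths, COVID-19 events, serious TEAEs, special-interest TEAEs and TEAEs leading to discontinuation, interruption or reduction. Other TEAEs and the worst laboratory grades cannot be divided by period from these outputs.

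**Dates.** The SAP gives no figure to reproduce: no group sizes, exposure, event rates, unblinding date or end date. It does give two dates: enrollment stopped on 03 MAR 2017 and amendment 6 is dated 01 DEC 2017. The interval is 273 days, and 273 / 30.44 = 9.0 months. If unblinding did not precede the amendment, the last patients enrolled had about 9 months or more before administrative closure, and earlier patients had longer. Late screening could shorten this slightly.

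**Size of the window part.** All rates are assumptions. Let h be the monthly event hazard, d the monthly discontinuation rate, T the months to placebo closure and E the further months for copanlisib. Both arms have the same h and d. The 30-day tail is ignored.

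- Incidence: CI(T) = h/(h+d) × (1 − exp(−(h+d)T)).
- Window part: CI(T+E) − CI(T) = exp(−(h+d)T) × CI(E). This is the share still on drug and event-free at unblinding, times their incidence in the added time. It is never negative.

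With h = 0.03, d = 0.10 and E = 12: CI(12) = 0.2308 × (1 − exp(−1.56)) = 18.2%.

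| Placebo closure | Still on drug and event-free | Placebo | Copanlisib | Window part | Patients in 20 |
|---|---|---|---|---|---|
| T = 9 | exp(−1.17) = 31.0% | 15.9% | 21.6% | 5.7 points | 1.1 |
| T = 12 | exp(−1.56) = 21.0% | 18.2% | 22.1% | 3.8 points | 0.8 |

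Across h of 1, 3 or 5%, d of 5, 10 or 15%, T of 9 or 12 and E of 6, 12 or 24 months, the window part runs from 0.6 points (h 1%, d 15%, T 12, E 6) to 18.5 points (h 5%, d 5%, T 9, E 24). With T = 12 the maximum is 13.7 points. These figures assume a constant hazard. For events confined to the first infusions, incidence in the added time is near zero, and so is the window part.

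**Net difference.** Unequal discontinuation can outweigh the window. Take h = 3% in both arms, d = 5% on placebo and 15% on copanlisib, T = 12, E = 12. Placebo shows 23.1% and copanlisib 16.4%, a difference of −6.7 points: +1.7 from the window and −8.4 from discontinuation.

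**The case against.** The strongest defence is that the plan is descriptive, open about its windows and deliberately simplified because few patients were enrolled. The objective is the safety of copanlisib, for which the full-period data are the right material. No difference, ratio or test is planned. Table layouts are left to sponsor standards that are not shown. Exposure is tabulated for the same groups, and the most consequential events are listed patient by patient. All of this stands and rules out any claim of a false test or of concealment. It does not make the cumulative columns like for like, and Section 6.3.4 displays results by treatment group.

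A second objection also stands: a cut at unblinding does not equalize exposure. In the reversal example the true hazards are equal, yet the cut moves the displayed gap from −6.7 to −8.4 points (14.7% against 23.1%). With d of 5% on copanlisib and 10% on placebo and h = 3%, 4.9 points remain at 12 months even after the cut. The fix must say so.

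Two stronger readings are tempting. A reader might infer that the tables necessarily overstate copanlisib's toxicity. Only the window part has a fixed sign; the net difference can go either way. A reader might also infer a very large distortion, from early placebo closure or from follow-up into 2020. Closure at 6 months would give 8.4 points in the middle case, but the enrollment and amendment dates make it unlikely. The March 2020 drug dictionary version and the COVID-19 listings suggest late data collection, but they do not show how long or how many randomized copanlisib patients stayed on drug.

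**Conclusion.** The point holds, at minor to moderate weight. As written, the SAP sets cumulative safety results from unequal windows beside each other, mixes blinded with open-label reporting in the copanlisib column, and contains no summary limited to the period before unblinding. The asymmetry after unblinding concerns only copanlisib patients still on drug at that moment, and the SAP does not give their number.

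Neither the size nor the net direction can be derived from the SAP. The middle-case figures of 5.7 and 3.8 points illustrate the window part alone. They rest on the assumed rates, a constant hazard equal in both arms, 12 further months on copanlisib, and unblinding no earlier than amendment 6.

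**What to change.** Keep the full-period tables. Footnote them to say that the columns cover unequal windows and that the copanlisib column includes open-label time.

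Add one copanlisib versus placebo TEAE overview covering any, Grade 3-5, serious, special-interest and hyperglycemia TEAEs. Count events up to each patient's unblinding date, or up to the switch at PD or the end of the TEAE window if earlier. Show copanlisib events after unblinding separately. The SAP does not say that an individual unblinding date was recorded for copanlisib patients; if it was not, use the study unblinding cut-off date.

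Report patient-time at risk beside the cut table, and state that the cut removes only the window and open-label difference, not unequal discontinuation before unblinding. A cut version of the worst-grade laboratory table is optional.

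The cost is SAP wording, a date cut and one or two extra tables with small numbers.

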6.1 Population characteristics

6.1.1 Disposition

Disposition will be described by randomized treatment group (Copanlisib / placebo) for overview and the study phases of screening, treatment, safety follow-up, active follow-up and survival follow-up. Primary reasons for discontinuation from each study phase will be summarized.

Disposition for overview and screening will be summarized for all enrolled patients. Disposition for treatment will be summarized for full analysis set. Disposition for safety follow-up will be summarized for safety analysis set.

6.1.2 Protocol Deviations

The summary table for patients with major and minor protocol deviations will be summarized for full analysis set. Listings for major protocol deviations and COVID-19 related protocol deviations will be provided.

6.1.3 Demographic and Baseline Characteristics at Study Entry

Demographics and baseline characteristics are documented on the electronic Case Report Forms (eCRFs) of Demography and vital signs at baseline.

The following demographics and additional baseline characteristics at study entry will be summarized for full analysis set:

- Age (Years) and Age group (years) <65 and >=65
- Sex
- Medical history of diabetic (Diabetic / Non-diabetic)
- Medical history of arterial hypertension (With / Without)
- Ethnicity (Not Hispanic or Latino / Hispanic or Latino / Not reported)
- Race (White / Black / Asian / American Indian or Alaska Native / Native Hawaiian or Other Pacific Islander / Not reported)
- BMI=weight (kg) / [height (m)]²

6.1.4 Cancer and Other Characteristics at Study Entry

Cancer and other baseline characteristics are reported on the eCRFs of Classification of Non-Hodgkin's Lymphoma, ECOG Performance Status, Systemic Anti-Cancer Therapy (Prior), Vital Signs at baseline, and Cardiac Disease (NYHA assessment).

The following cancer and other baseline characteristics will be summarized for full analysis set:

- Histology of tumor at study entry
- Follicular lymphoma (FL) grade at study entry, if FL
- Follicular Lymphoma International Prognostic Index (FLIPI) (5) score (for patients with FL) at study entry
- Staging of tumor (Ann Arbor classification) at study entry
- Number of prior systemic cancer therapy lines (1-3, 3-5, >5)

Statistical Analysis Plan

BAY 80-6946 / 17322

Page: 12 of 20:

- Infiltration seen in bone marrow biopsy as per local assessment
- Time from initial diagnosis to randomization (months)
- Time from most recent progression to randomization(months)
- Time since first progression to randomization (months)
- Number of baseline target lesions (Total number and frequency by group 1-3, 4-6)
- Number of baseline non-target lesions (Total number and frequency by group 1-3, 4-6, 7-8, >8)
- Serum IgM level (for WM only) (mg/dL) at baseline
- Baseline Eastern Cooperative Oncology Group (ECOG) performance status
- New York Heart Association (NYHA) classification (Class I / Class II / Class III / Class IV / Not applicable) at baseline
- Systolic Blood Pressure (mmHg) at screening
- Diastolic Blood Pressure (mmHg) at screening
- Baseline HbA1c

6.1.5 Medical History

Medical history (i.e., relevant previous diagnoses, diseases or surgeries) not pertaining to the study indication, that started before signing of the informed consent and considered relevant to the study will be presented by MedDRA version 22.1 or higher Primary System Organ Class (SOC) and Preferred Term (PT). All medications and significant non-drug therapies taken within 30 days (window of +5 days allowed) before study entry will be recorded and summarized for full analysis set.

6.1.6 Prior and Concomitant Medication

Prior and concomitant medications will be coded by the *World Health Organization Drug Dictionary* (WHO-DD) Version MAR 2020 or higher.

Prior and concomitant medications will be summarized based on WHO-DD Anatomical-Therapeutic-Chemical (ATC) drug class and drug name for full analysis set.

Any medication that has been stopped after first administration of study treatment (Copanlisib/ placebo) is considered as concomitant and otherwise as prior. Note that the same medication can appear more than once in the table as it can have several ATC codes.

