4.3 Handling of Missing Data

In order to achieve the goal of a well conducted clinical trial according to Good Clinical Practice (GCP), every effort should be made to collect all data. However, despite best efforts, it may be inevitable that missing or incomplete data are reported. All missing or partial data will be presented in the patient data listing as they are recorded on the Case Report Form (CRF). Unless noted, missing data will not be estimated or carried forward in any statistical analysis.

The general principle for imputing dates is as follows:

If an adverse event start date is completely missing or partially missing, then it is assumed that the start date occurs at the earliest time on-treatment whenever possible.

If a concomitant medication date is completely missing or partially missing, then the stop date is imputed to maximize the duration of the concomitant treatment. It should be noted that imputation of stop dates only applies to concomitant medications that are not ongoing.

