4.5 Data Rules

If time intervals are to be displayed other than days in statistical evaluations, then one year is considered to have 365.25 days (average length of a year, including leap years), one month is considered to have 30.44 days (average length of a month, including leap years), one week is considered to have 7 days, and one cycle is considered to have 28 days (i.e. 4 weeks).

Baseline

Baseline is defined as the last available measurement performed prior to the first dose of Copanlisib/placebo study drug administration at Cycle 1 Day 1 for the patients who initially received Copanlisib/placebo. For the patients who initially received placebo and switched to Copanlisib after unblinding, baseline is defined as the last available measurement prior to the first dose of Copanlisib after switching.

Repeated measures

Statistical Analysis Plan

BAY 80-6946 / 17322

Page: 10 of 20:

If there are repeated measurements per time point (e.g. laboratory values, vital signs, etc.), the following rules will be used (unless otherwise specified):

- Before the start of the study drug administration (i.e., for screening and baseline value), the latest measurement at scheduled visits will be used. Unscheduled visits will be used, if there are no measurements at pre-baseline or baseline scheduled visits. If the latter is the case, the last unscheduled visit will be used.
- In case of repeated measurements at any post-baseline time point, the first value of the scheduled measurements at that time point will be used. No unscheduled measurements will be used for any time points besides screening / baseline even when measurements at scheduled visits are missing.

5. Analysis Sets

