6.3.4 Hyperglycemia

Hyperglycemia adverse events using specific MedDRA PT grouping ‘MLG Hyperglycemia’ will be summarized by treatment group and by NCI CTCAE worst grade for TEAEs and TESAEs.

In addition to the above summary, specific HbA1c evaluation will be performed for each analysis group including at baseline and post-baseline-mean, classified by diabetic/non-diabetic.

Patients will be categorized according to their baseline HbA1c values as

- < 5.7%
- $\geq 5.7\% - < 6.5\%$
- $\geq 6.5\%$.

Within each group, the descriptive statistics for HbA1c values at end of treatment visit will be summarized by treatment group and medical history of diabetic/non-diabetic. Shift table for classified HbA1c values from baseline to end of treatment by treatment group and medical history of diabetic/non-diabetic will also be provided.

Glucose in CTCAE grade will be displayed by treatment group and medical history of diabetic/non-diabetic at pre-dose and at post-dose 0 h, 1 h and 2 h after the end of study drug infusion on Cycle 1 Day 1 and at pre-dose and at post-dose 1 h after the end of study drug infusion on subsequent visit.

For patients with hyperglycemia adverse events, the number of patients using antihyperglycemic treatment with drug start date on or after their first treatment-emergent adverse event will be summarized in overall, and separately for the WHO-DD ATC classes for a) insulin and analogues and b) Blood glucose lowering drugs, excluding insulins. In addition, these summaries will be presented separately for the subgroups of patients with vs without history of diabetes.

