6.3.6 Hypertension

The blood pressure measurements will be recorded on the vital sign eCRF:

- Systolic blood pressure (mmHg, measured at 0 h (pre-dose), 30 min (mid-infusion), 60 min (end of infusion); and 1 h and 2 h after the end of infusion on infusion days)

Statistical Analysis Plan

BAY 80-6946 / 17322

Page: 18 of 20:

- Diastolic blood pressure (mmHg, measured at 0 h (pre-dose), 30 min (mid-infusion), 60 min (end of infusion); and 1 h and 2 h after the end of infusion on infusion days)

The number of patients with abnormal post-dose systolic/diastolic blood pressure will be displayed by visit and worst post-dose TEAE hypertension grade by treatment group and medical history of arterial hypertension/no medical history of arterial hypertension. For this purpose post-dose systolic/diastolic blood pressure values will be categorized according to CTCAE, version 4.03: Grade 1 (systolic 120-139 mmHg or diastolic 80-89 mmHg); Grade 2 (systolic 140-159 mmHg or diastolic 90-99 mmHg); Grade 3 (systolic \geq 160 mmHg or diastolic \geq 100 mmHg), grade 4 Life-threatening consequences; urgent intervention indicated.

Hypertension adverse events will be presented using MLG grouping of MLG Hypertension for TEAEs and TESAE,

For patients with hypertension adverse events, the number of patients using antihypertensive treatment with drug start date on or after their first treatment-emergent adverse event will be summarized descriptively. In addition, the number of patients requiring antihypertensive treatment will be presented separately for the subgroups of patients with vs without history of hypertension.

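### SAP 6.1.6 as written classes ongoing medication as prior, and it states no reference date for the concomitant-medication summary of patients who switched from placebo

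*SAP*

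**What the plan says.** SAP 6.1.6 tabulates prior and concomitant medication in the full analysis set by ATC class and drug name. Its whole classification rule is: "Any medication that has been stopped after first administration of study treatment (Copanlisib/ placebo) is considered as concomitant and otherwise as prior". It has no clause for ongoing drugs and none for patients who switched.

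SAP 4.3 imputes missing or partial stop dates so as to give the longest duration, with a limit: "It should be noted that imputation of stop dates only applies to concomitant medications that are not ongoing".

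SAP section 6, repeated in section 7, adds a separate set of summaries for those who moved from placebo to active drug: "Disposition, protocol deviations, concomitant medication, concomitant anti-cancer therapy, drug exposure, efficacy and safety variables will also be summarized separately for patients who switched". Concomitant medication is on that list; prior medication is not. Section 6 also ends the placebo group's period at the switch.

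Other sections state a new starting point for switchers. For adverse events, 6.3.1 dates it from the switch: "For the patients switching from placebo to Copanlisib, the start of study drug administration is referring to the start of Copanlisib drug administration". For a switch after unblinding (4.5): "baseline is defined as the last available measurement prior to the first dose of Copanlisib after switching". In 6.2, progression-free survival in switchers is counted from the start of copanlisib.

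**The concern.** There are two gaps in one rule.

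First, the only route to the concomitant class is a stop after first dose, and everything else is prior. A drug taken throughout treatment and never stopped therefore goes into the prior table, as does a drug started weeks into treatment that is still being taken. This is at odds with 4.3, whose limit on imputation makes sense only if some concomitant drugs are ongoing.

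Second, the switcher summary is meant to describe the copanlisib period after placebo, but 6.1.6 offers only the first dose of copanlisib or placebo and does not say which dose counts for these patients.

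At stake is whether the medication tables show what patients were taking on treatment. If the sentence is programmed as it stands, concomitant use is under-counted, prior use is over-counted, and the switcher table mixes two periods.

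**Working it through.** The SAP gives no figure on this point, so there is none to reproduce. The check applies the sentence in 6.1.6 to each possible timing. The days are illustrative and do not come from the SAP; first dose is day 0.

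**Rule as written:** concomitant if a stop exists and stop > 0; otherwise prior.

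- Stopped before day 0: prior. Correct.
- Started before day 0, stopped after it: concomitant. Correct.
- Started day 20, stopped day 40: 40 > 0, concomitant. Correct.
- Started before day 0, never stopped: no stop exists, so prior. Wrong in the light of 4.3.
- Started day 20, ongoing: no stop exists, so prior. Wrong in the light of 4.3.

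**Does imputation under 4.3 rescue the last two?** No. It excludes ongoing drugs, so they never receive a stop date. The two rules together even reverse the sensible order: a drug whose stop date is unknown is given the longest duration and can become concomitant, while a drug known to continue becomes prior.

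**Switcher, placebo from day 0, copanlisib from day 100:**

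- Drug taken days 10 to 30. With the first placebo dose as reference, 30 > 0, so it is concomitant in the switcher summary, although it was never taken with copanlisib. It is also concomitant in the placebo-group summary: 2 entries. With day 100 as reference, 30 < 100, so it is prior to the copanlisib period: 1 entry, in the placebo group only.
- Drug started day 110, ongoing. As written it is prior whichever reference is used. The switcher summary lists no prior medication, so it has 0 entries there. If ongoing drugs count as concomitant, it has 1.

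**Comparison with the other switcher rules.** SAP 4.5 also speaks of copanlisib/placebo when it defines baseline, yet adds a separate sentence for patients who switch after unblinding. SAP 6.2 and 6.3.1 likewise state their reset. SAP 6.1.6 has no such sentence.

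**The case against.** The best defence is that the authors plainly meant medication not stopped before first dose. Any later stop of an ongoing drug must fall after first dose, and 4.3 shows that the SAP thinks of ongoing drugs as possibly concomitant. SAP 4.1 also refers to sponsor standards that are not shown and may hold the correct derivation. The intent is probably as described, and 4.3 conflicts with 6.1.6 only by implication, since it defines neither class. But the written rule is explicit, makes prior the remaining class, and can be programmed literally. Standards that are not shown cannot be relied on to correct it.

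On switchers, it can be said that 6.1.6 is silent rather than wrong: the reference to copanlisib/placebo could mean whichever drug belongs to the group being summarised, and the resets elsewhere point to the same convention. This stands in part. A reader might infer that 6.1.6 positively fixes the first placebo dose as reference for switchers. It does not; it leaves the reference unstated. The double entry shown in the working also assumes that records from before the switch are fed into the switcher summary, which section 6 does not say.

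A reader might also infer that 6.1.6 contradicts the counts in 6.3.4 ("the number of patients using antihyperglycemic treatment with drug start date on or after their first treatment-emergent adverse event") and 6.3.6 ("the number of patients using antihypertensive treatment with drug start date on or after their first treatment-emergent adverse event"). The SAP does not support this. Those counts are restricted to patients with the adverse event concerned and select drugs by start date. The tables in 6.1.6 cover all medication in the full analysis set with no such conditions. They need not agree under any wording.

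**Conclusion.** The concern holds, as a minor one. As written, 6.1.6 classes ongoing medication as prior, including drugs started on treatment, against the clear implication of 4.3. It also leaves the reference date for the switcher summary unstated, where adverse events, progression-free survival and baseline after an unblinding switch each have one.

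The effect is limited to descriptive medication tables in a curtailed study with descriptive analyses only. A reader might take it as a threat to the safety results, but no endpoint, adverse-event derivation, or count in 6.3.4 or 6.3.6 depends on the flag. The number of records or patients affected cannot be derived from the SAP; the days in the working show only the direction. Drugs ongoing at first dose and stopped later are classed correctly.

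The first part rests on the sentence being applied literally. The second rests also on the first placebo dose being taken as reference for switchers, which the text permits but does not require.

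**What to change.** Replace the rule in 6.1.6 with wording such as:

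> A medication is concomitant if it is ongoing (no stop), or if its stop date, after imputation under 4.3, falls on or after the date of the first study-treatment dose. Otherwise it is prior. For patients never dosed, all medication is prior. In the summary of patients who switched from placebo, the first dose is the first copanlisib dose after the switch.

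Two details matter. The full analysis set is all randomized patients and so may include some who were never dosed; the rule must keep a class for their medication, as the present catch-all does. And saying on or after settles a stop on the day of first dose, which the present wording leaves unclear when only dates are recorded.

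The cost is one reworded rule, one sentence for switchers and one changed derivation. No data need to be collected or altered.
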